5.0 OVERALL STUDY DESIGN AND PLAN: DESCRIPTION

5.1 Overview of Study Design

This is a single-center, single-arm, open-label study conducted at the University of Michigan's Chronic Pain and Fatigue Research Center (Figure 4). Patients with stage 0-III breast cancer who have chronic pain that developed or worsened since breast cancer diagnosis and whose worst pain is rated at least 5 on a 10 point Likert-type scale and who meet the other inclusion and exclusion criteria outlined in Sections 5.4 and 5.5 will be eligible to enroll in the study.

Patients with chronic pain (cases) who qualify for the study at Screening will begin a 1- to 4-week washout period (if necessary) to taper off antidepressants and other drugs that they are currently taken and that cannot be taken along with duloxetine therapy. Patients who successfully taper off all excluded medications and continue to meet all of the inclusion criteria (and no exclusion criteria) at Baseline/Randomization (Visit 1) will start treatment with duloxetine as indicated below and will undergo serial comprehensive assessment with questionnaires and QST. Patients will receive 7 weeks of duloxetine (1 week of 30 mg/d, 4 weeks of 60 mg/d, and 2 weeks of 30 mg/d). QST and questionnaires will be completed prior to initiation of treatment and after 5 weeks of treatment, before reduction in dose to 30 mg/d. Patients who are tolerating duloxetine well, want to continue therapy using commercial supply, and do not want to taper off duloxetine will not be required to take the final 2 weeks of 30 mg/d.

The duration of participation in this study for cases with chronic pain will be 5-11 weeks, depending on the time required for patients to taper off excluded medications and depending on if patients wish to remain on commercial duloxetine following assessment #2. This study will randomize approximately 84 patients with chronic pain.

Control subjects (n=48) who meet all eligibility criteria but who have average pain 0-1 on a 10 point scale will undergo assessment with questionnaires and QST at a single timepoint.

In order to account for treatment heterogeneity, for both the case and control cohorts subjects will be enrolled in equal numbers into the following treatment "bins": (1) surgery +/- radiation therapy, (2) surgery and chemotherapy +/- radiation therapy, (3) surgery and endocrine therapy +/- radiation therapy, (4) surgery, chemotherapy, and endocrine therapy +/- radiation therapy.

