5.4 Inclusion Criteria

To be eligible to participate in this study as a case, patients must meet the following criteria:

1. Written informed consent obtained from the patient before the initiation of any study-specific procedures
2. Female patients at least 25 years of age
3. Diagnosis of stage 0-III breast cancer within 12 years prior to enrollment. All indicated surgery, chemotherapy, and/or radiation therapy must have been completed at least 12 weeks prior to enrollment. Concomitant endocrine therapy and trastuzumab are permitted.
4. Pain that developed or worsened since breast cancer diagnosis and is not due to identifiable traumatic event or fracture
5. Patient-reported worst pain score between 5 and 10 (inclusive) on a 0-10 scale (assessed verbally)
6. Female patients must be at least 1 year postmenopausal or surgically sterile; or must agree to use a medically acceptable form of contraception
7. Willing to withdraw from selective serotonin reuptake inhibitors and tricyclic antidepressants prior to treatment initiation
8. Patients who are currently taking NSAIDs and/or opioid pain medications must remain on a stable dosage throughout the duration of the study

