5.5 Exclusion Criteria

Patients who meet any of the following criteria will not be eligible to participate in the study as a case:

1. Prior use of duloxetine or milnacipran.
2. Prior use of venlafaxine specifically for treatment of pain (prior use for treatment of other indications, such as hot flashes, is permitted)
3. Patients must not be taking any contraindicated medications listed on the duloxetine package insert including the following: phenothiazines, propafenone, flecanide, linezolid, or anticoagulation medication (e.g., heparin, warfarin); treatment with MAO inhibitor within 14 days prior to registration
4. Thumbnail abnormalities on either hand (such as due to chemotherapy or trauma, or artificial nails) that are likely to alter pain perception during testing
5. Peripheral sensory neuropathy at the thumbs bilaterally that interferes with function and/or activities of daily living
6. Significant risk of suicide based on the Investigator's judgment
7. History or behavior that would, in the Investigator's judgment, prohibit compliance for the duration of the study.
8. History of alcohol or other substance abuse or dependence within the year prior to registration
9. Known chronic liver disease, end stage renal disease, or creatinine clearance <30 mL/min as defined by Cockcroft-Gault equation
10. Uncontrolled narrow-angle glaucoma.
11. Clinically significant coagulation disorder
12. Pregnant or breast-feeding. Urine pregnancy test will be assessed at the baseline visit in women of child-bearing potential with chronic pain.
13. Unable to take oral medications or any medical condition that would interfere with the absorption of study medication capsules.

Controls are patients without chronic pain who otherwise meet the following eligibility criteria (inclusion #1-3, exclusion #1, 2, 4, 5, worst pain score 0-1, and not currently on medication for pain)

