9.0 Outcome Measures

9.1 Primary Outcome Assessment

9.1.1 Brief Pain Inventory

The Brief Pain Inventory (BPI) is a 17-item patient self-rating scale that assessed sensory and reactive components of pain.⁶⁹ For sensory components, it addresses severity, location, chronicity, and degree of relief due to therapy. For reactive components, it assesses depression, suffering, and perceived availability of relief. Reliability has been demonstrated over short intervals using test retest item correlation; worst pain, $r=0.93$, usual pain, $r=0.78$, pain now $r=0.59$. It has been validated in patients with both cancer and non-cancer pain.^{76,77} Ratings of pain interference with various activities increased as ratings of pain severity were higher. The proportion of patients receiving opioid analgesics also increased with increased severity rating.

The BPI uses 0 to 10 numeric rating scales for item rating because of its simplicity and lack of ambiguity. Since pain can be variable over a day, the BPI asks patients to rate their pain at the time of completing the questionnaire, and also at its worst, least, and average over the previous 24 hours. The primary endpoint for this clinical trial will be based on the 24-hour average pain as reported on the BPI. The ratings can be combined to give a composite index of pain severity. Also, using numeric 0 to 10 scales, with 0 being “no interference” and 10 being “interferes completely”, the BPI asks for ratings of the degree to which pain interferes with mood, walking and other physical activity, works, social activity, relations with others, and sleep. The mean of these scores can be used as a pain interference score.

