This variable will be used as an effect modifier in a regression model linking the primary response of pain severity and other response variables with the phenotype variables. The resultant mixture of regression models where the latent centrality variable will be shared by all regression models within the subject will be fit by the EM algorithm with iterative imputation of the latent centrality status. Regression models for each response variable will be of the generalized linear models (GLM) family. The data will have ample information to bear on the distribution of patients over the latent classes as the model will borrow strength from all contributing GLMs. The model will be refined in layers by adding response and predictor variables deemed informative of the latent centrality. The performance of the model will be measured by the Akaike Information Criterion (AIC). A threshold of 2 per 1 degree of freedom will be applied to AIC differences between models as a measure of significant difference between models. The model showing the highest AIC will be selected as the best model for subsequent analysis and prediction. The latent centrality status will be predicted for each subject by a Bayesian argument using the best model. Continuous, ordered categorical and binary latent centrality status will be explored in search for the model that provides the best explanation for the heterogeneity of pain responses in the breast cancer survivors.

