As an illustration of the method we fitted a binary centrality status (central vs. non-central) model (a mixture of two different latent linear regression models specific for the centrality class) to cross-sectional pain severity data on 199 breast cancer patients from an unpublished cross-sectional study we conducted on breast cancer survivors 1-3 years following diagnosis. PainDETECT, age, BMI, HADS depression and anxiety, sleep disturbance, fatigue, Perceived Stress Scale, and treatment bin (listed in Figure 4) were used as explanatory phenotype variables. The model resulted in identification of two clusters (cluster 1: 64% of patients; cluster 2: 36%) of breast cancer patients defined by dissimilar regression relationships between pain and phenotype and clinical variables. Cluster 2 is characterized by persistently higher levels of pain (Figure 5). Age, BMI and fatigue are significant variables in Cluster 1 while neuropathic pain and depression mark Cluster 2 regression. While in the data analysis we will favor continuous characterization of centrality, this binary model is used as a source of information for the power analysis below. Using the AIC criterion, the two-cluster model is significantly better than the homogeneous patient population (one regression, no latent heterogeneity explained by centrality). We note that treatment was not significant ($p=0.39$), in line with our hypothesis of common pain mechanism regardless of the type of insult.

Analysis. The planned sample size for Aim 1 is 132 (84 cases and 48 controls). For Aim 2, latent dichotomous pain centrality status will be hypothesized and regressed on explanatory variables including the ones involved in the CNS pain regulation. We will assume that the causality of the effect of the centrality block of variables on the Duloxetine (DLX) treatment outcome will follow through the centrality status. In addition to the random effect representing the interaction between the drug effect and the

[figure not shown]

Fig. 5. Clustering of 199 BCS using a mixture of 2 (pain ~ phenotype + treatment + demographics) regression models. Red high pain latent cluster is loosely identified with predicted centralized pain classification, and the blue cluster with non-centralized. Note that none of the phenotype variables taken alone serves as a particularly good surrogate for the classification, and the mixture approach that borrows strength across various phenotypes is essential.

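### A two-class centrality status fitted to cases and controls together would be pulled toward the entry rule and label too many cases central

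*Combined protocol and SAP*

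**What the plan says.** - **Entry of cases (5.4):** "Patient-reported worst pain score between 5 and 10 (inclusive) on a 0-10 scale (assessed verbally".
- **Entry of controls (5.3 and 5.5):** "worst pain score 0-1, and not currently on medication for pain". Section 5.1 differs and describes controls as women "who have average pain 0-1 on a 10 point scale will undergo assessment".
- **Sample for Aim 1 (11.0, Analysis):** "The planned sample size for Aim 1 is 132 (84 cases and 48 controls".
- **Model (11.0, Exploratory analyses):** BPI pain severity is listed among the measures that inform latent centrality. The latent variable then acts as an effect modifier in a "regression model linking the primary response of pain severity and other response variables with the phenotype variables". The covariates named are demographic variables and treatment bin.
- **Form of the status:** continuous, ordered categorical and binary forms will all be explored. The plan prefers a continuous one, but Aim 2 is written for a dichotomous status.
- **Illustration:** 199 survivors from a cross-sectional study, with no selection on pain described. The Figure 5 caption reads: "Red high pain latent cluster is loosely identified with predicted centralized pain classification".
- **Role of controls (opening of 11.0):** to define differences between the two cohorts and to help interpret change in treated women.

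**The concern.** A mixture model looks for groups that explain the spread in its responses. Here one group boundary is put in by sampling: worst pain is high in every case and near zero in every control, whatever the biology. With pain as the leading response and no term for case status, a two-class solution can take up that boundary in place of a difference among women with chronic pain.

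Objective 1 asks about centralization in survivors with chronic pain. If the boundary leaks into the classes, the share of cases called central is inflated by the entry rule. The pilot fit does not speak to this, because no such gap is described in its sample. For Aim 2 the plan hypothesizes response rates of at least 70% in central and 10% in non-central patients, and a central class filled with non-central cases would dilute that difference.

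**Working it through.** **1. The plan's own figures.** 84 + 48 = 132 (the Synopsis gives approximately 124, which does not match). Overall response: 0.30 × 0.70 + 0.70 × 0.10 = 0.28. Power for 28% against 6% with n = 21, two-sided 0.05, arcsine method: h = 2·asin(√0.28) − 2·asin(√0.06) = 0.620; 0.620 × √21 − 1.96 = 0.88; Φ(0.88) = 0.81. The stated 81% reproduces. It concerns response within a treatment bin, not central against non-central patients, so it does not bear on this point.

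**2. How much of pooled worst pain is the entry rule.** This takes the BPI worst-pain score to equal the entry score. Let p = 84/132 = 0.636 and p(1−p) = 0.2314. The share of variance explained by case status is B/(B+W), with B = p(1−p)(m₁−m₀)² and W = p·v₁ + (1−p)·v₀.
- Scores uniform within each range: m₁ = 7.5, v₁ = 35/12 = 2.917; m₀ = 0.5, v₀ = 0.25. B = 0.2314 × 49 = 11.34; W = 0.636 × 2.917 + 0.364 × 0.25 = 1.95. Share = 85%.
- Least favourable distribution: for a given mean the largest variances are (m₁−5)(10−m₁) and m₀(1−m₀). The minimum is near m₁ = 6.54, m₀ = 1: B = 0.2314 × 5.54² = 7.10; W = 0.636 × 1.54 × 3.46 = 3.39. Share = 68%.

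So at least about 68% of the variance in pooled worst pain is set by enrolment.

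**3. The limiting case.** If the classes coincided with case status, the high class would hold 84/132 = 64% of the sample. Under the plan's 30%, about 0.30 × 84 = 25 cases are central, which is 25/132 = 19% of the pool. This is a bound, not the expected result.

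**4. Simulation, main setting.** The documents give no phenotype shifts or correlations, so these are assumptions: 30% of the 84 cases central, no control central, worst pain as the score, 6 or 15 phenotypes, within-group correlation 0.2, central shift 0.5-1.0 SD, case-control shift 0.5 SD.

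| | Pooled | Cases only, or pooled with case status as covariate |
|---|---|---|
| Two classes: cases in high class (true 30%) | 56-83% | – |
| Two classes: accuracy among cases | 0.42-0.71 | 0.64-0.83 |
| Continuous status: AUC among cases | 0.73-0.92 | 0.73-0.92 |

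The pooled two classes agreed with case/control status in 0.69-0.87 of women, and in about 0.57 when there was no case-control shift. Calling every case non-central would score 59/84 = 0.70, so the low end of the right-hand column is no success either.

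**5. Simulation, other settings** (pain plus eight scores, 20-40 replicates each).
- Two-class multivariate model, worst pain: all cases in one class at central shifts up to 0.5 SD and 80-100% at 1 SD. At 1.5 SD it found centrality (29-44% of cases in the high class), unless the case-control shift was 1 SD (90%).
- Two-class mixture of regressions of pain on four of the scores, worst pain: agreement with case status 0.94-1.00 at a case-control shift of 0-0.5 SD, and 0.67-0.79 at 1 SD.
- Average pain instead (central shift up to 1 SD): agreement 0.80-0.99 for the multivariate model and 0.74-0.95 for the regression mixture.
- Three classes, worst pain, central shift 1 SD or more: preferred to two by AIC in every replicate, with agreement of 0.90-0.98 with true centrality among cases.
- Pooled continuous score, worst pain: AUC among cases 0.86 at 0.5 SD and 0.97-1.00 at 1 SD or more.

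**6. What mislabelling would do to the Aim 2 contrast, if the classes were carried forward.** 56-83% of 84 is 47-70 cases in the high class. Suppose, most favourably, that all 25 central cases are among them. Response in the high class is then (25 × 0.70 + 22 × 0.10)/47 = 42%, or (25 × 0.70 + 45 × 0.10)/70 = 31%, against 10% in the low class. The planned 70% against 10% shrinks to at most 42% or 31% against 10%.

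**The case against.** A reader might infer that the pooled fit simply returns case/control status, so that all treated women share one class and Objective 2 has no predictor. The documents do not support that, for four reasons, all of which stand.

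- The plan prefers a continuous status and will also try ordered categories. In the simulations the continuous score lost no discrimination among cases, and three classes recovered centrality when separation was good.
- No sentence carries classes from a pooled Aim 1 fit into Aim 2. Aim 2 is described separately, with a drug-effect interaction and repeated measurements, to which untreated controls seen once contribute nothing.
- The BPI item meant by pain severity is not named. Section 9.1.1 says: "The primary endpoint for this clinical trial will be based on the 24-hour average pain as reported on the BPI". Section 11.0 makes worst pain primary. Average pain has no minimum for cases, and the Amendment 6 entry notes that it is often low in candidates, so the gap may partly close.
- The Figure 5 label belongs to a pilot illustration and is hedged. It is not a classification rule for the trial.

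The work is also listed as exploratory, and the primary outcome, change in worst pain in treated women, is untouched. The 64% in step 3 and the plan's 30% of the breast cancer population have different denominators, so they should not be read as a direct comparison.

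What remains is that a binary form is among those to be explored and is the form named for Aim 2, the Aim 1 sample is stated as the pooled 132, and nothing in the plan handles case status.

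**Conclusion.** The point holds for a binary status fitted to the pooled sample. The entry rules fix at least about 68% of the variance in pooled worst pain, and the two-class solution is then drawn toward the enrolment strata. In the main simulations 56-83% of cases were labelled central against a true 30%. That biases the binary answer to Objective 1. Harm to Aim 2 is conditional on those classes being carried forward.

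The direction of the bias is clearer than its size. The figures rest on assumed central and case-control shifts, within-group correlation, number of phenotypes and BPI item, on few replicates per setting, and on models simpler than the plan's shared set of generalized linear models. With no case-control shift, or with a central shift of 1.5 SD, the pull was weak in some settings. In others nearly all cases fell in one class. A claim that no contrast among treated cases survives would go too far.

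**What to change.** In Section 11.0:
1. Fit the latent centrality model in the 84 cases. Use the 48 controls as the reference for standardising the QST, body-map and symptom scores and for direct case-control comparison, which is the role the opening of the section already gives them. If a pooled fit is kept, include case/control status as a fixed covariate in every response model.
2. Name the BPI item used as pain severity, and reconcile Sections 5.1, 5.3 and 5.5 on whether controls are defined by average or worst pain.
3. State that the dichotomous status in Aim 2 comes from this fit, and amend the Aim 1 sentence to say which women enter the latent model.

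The cost is wording, with no new data. A cases-only fit uses 84 rather than 132 women. Neither version recovers centrality well if the phenotypes separate central from non-central cases by about 0.5 SD or less: in the eight-score simulations the cases-only fit then reached 0.58-0.69 agreement, no better than the 0.70 from calling every case non-central. The plan should acknowledge that limit.

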central status, subject specific random intercept will be introduced to model correlation due to repeated measurements. A generalized linear mixed model will be used with the two response variables (self-report pain questionnaires and experimental pain testing scores). The form of the link function and variable transformations will be determined based on the data using AIC criteria. A full likelihood model-based approach will be used to fit the model. Hypotheses will be tested by the likelihood ratio test. A clinically relevant response is defined as 50% reduction in pain within the patient. The following effects are hypothesized based on our pilot studies: Central patients will constitute approximately 30% of the breast cancer population; 10% of non-central patients are hypothesized to show clinically relevant improvement under DLX while the rate of at least 70% is hypothesized in the central group. Overall, this leads to the expected 28% response rate. Placebo effects in this kind of studies are expected not to exceed 3%. Conservatively we would be looking to detect improvement over twice the expected placebo rate (6%). Using a two-sided test for the proportion of improvement vs. 6% at $\alpha=0.05$ we will have the power of 81% with 21 patients in each "bin" (total of 84 patients).

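### Section 11.0 does not keep week-5 on-drug scores out of the estimation of central status, so for Aim 2 a class difference in response would not show that baseline centralization predicts response

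*Combined protocol and SAP*

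**What the plan says.** Two parts of section 11.0 bear on this point.

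**Exploratory analyses, assessment of centralized pain.** A latent centrality variable is shared by all of a subject's regression models and fitted by EM. A model is chosen by AIC for later analysis and prediction, and each subject's status is then predicted from that model. The text does not say whether that prediction uses Visit 1 data alone.

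**Analysis, Aim 2.**
- The status: "latent dichotomous pain centrality status will be hypothesized and regressed on explanatory variables including the ones involved in the CNS pain regulation".
- A term linking status to drug effect, in the sentence that opens "In addition to the random effect representing the interaction between the drug effect and the" and ends, after the Figure 5 legend, with central status.
- Within-woman correlation: "subject specific random intercept will be introduced to model correlation due to repeated measurements".
- The outcomes: "A generalized linear mixed model will be used with the two response variables (self-report pain questionnaires and experimental pain testing scores").
- Estimation and testing: "A full likelihood model-based approach will be used to fit the model" and "Hypotheses will be tested by the likelihood ratio test". The hypotheses to be tested are not named.

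Section 5.1 places these measurements before treatment and after 5 weeks of duloxetine. The sample size paragraph supposes that about 30% of patients are central and 10% of non-central patients respond, "while the rate of at least 70% is hypothesized in the central group". Response is a 50% reduction in pain.

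**The concern.** A predictor has to be known before treatment starts. If a woman's class is inferred in a model where the classes may differ in drug effect, and her on-drug scores are in that likelihood, her own response helps to place her. The fit can gather women who improved into one class, whether or not anything at baseline set them apart. If that class is then called central, its better response follows from how it was formed.

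Identifying predictors of response is one of the two objectives in section 3.0, and this is the only described analysis that relates centrality to duloxetine response. The design is single-arm, so there is no comparator group in which a spurious class could be recognised.

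**Working it through.** **1. The plan's own figures.** Overall response: 0.30 × 0.70 + 0.70 × 0.10 = 0.28, as stated. Power for 28% against 6%, two-sided α = 0.05, n = 21 per bin, by the arcsine formula: h = 2·asin(√0.28) − 2·asin(√0.06) = 1.115 − 0.495 = 0.620; Φ(0.620 × √21 − 1.96) = Φ(0.88) = 0.81. The stated 81% reproduces. It concerns a response rate within a bin and tests neither central status nor any predictor.

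**2. Why on-drug scores can drive the class.** Take one outcome with change d, baseline variables x, P(class 1 | x) = logit⁻¹(α + βx), and d normal with mean μ₁ or μ₀ by class and common variance σ². The posterior log odds of class 1 are

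α + βx + [(μ₁ − μ₀)/σ²] × [d − (μ₁ + μ₀)/2].

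If no baseline variable predicts response, β = 0 and only d sorts the women.

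**3. Size under the null.** Inputs from the documents: 84 cases, scores at baseline and week 5, two outcome types, a two-level status, 50% reduction as response, about 28% responding. Assumed, because the documents do not give them: the SDs and the shape of the change. Two shapes were used: two groups (as the plan hypothesises) and a single hump (no true classes). Response was independent of every baseline variable. A two-class model was fitted by EM to 150 trials per setting. In the Aim 2 form, with status regressed on baseline variables, the better-responding class was labelled central. The test of class difference was Fisher's exact at 5%.

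| Aim 2 form, 2 or 8 regressors | Two-group response | Single hump |
|---|---|---|
| Share in 'central' class | 29-34% | 49-52% |
| Response, 'central' | 78-89% | 47-53% |
| Response, other class | 4-9% | 7-11% |
| Class agrees with responder status | 83-93% | 62-67% |
| False class difference | 91-100% | 71-89% |
| LRT of regressors rejects, 2 regressors | 7-11% | 10-14% |
| LRT of regressors rejects, 8 regressors | 15-21% | 42-49% |

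A simpler fit with one outcome and four null covariates gave 92% versus 3% with a two-group response. A further null run gave 96% versus 4% (two-group) and 53% versus 6% (single hump). The combined ranges are therefore 78-96% versus 3-9%, and 47-53% versus 6-11%.

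**4. Same trials, status from baseline data only.** A false class difference appeared in 1-5% of trials.

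**5. A different model form.** Eight phenotype measures were entered as class indicators, with real baseline classes unrelated to response and the class labelled by baseline level.
- Separation 1.2 SD: the class matched the baseline class in 95% of women, response was 28-29% in both classes, and a false difference appeared in 5-9% of trials.
- Separation 0.7 SD: a false difference in 50-61% of trials. Average rates were close (38% versus 37%; 27% versus 29%), so the false differences went in both directions.
- No separation: a false difference in 80-93% of trials.

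**The case against.** **The text may intend two stages.** Section 11.0 speaks of choosing a model for later analysis and prediction, the Aim 1 sample includes 48 controls measured once, and the worked illustration is cross-sectional. Estimating status at baseline and carrying it into Aim 2 is a plausible intention. It is nowhere stated, and the Aim 2 paragraph describes a latent status inside a repeated-measures likelihood. So the objection shows ambiguity and does not remove the problem.

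**The fitted class need not be the responders.** A reader might infer that it always is. The documents do not support that. It comes close only with a two-group response. With a single hump, about half of the 'central' class are not 50% responders, and with strong baseline indicators the class follows baseline. Section 11.0 does describe the measures as a multivariate phenotype informing latent status, so that last case is relevant. This part of the objection stands.

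**70% versus 10% is not a planned test.** A reader might take it as one. It is a hypothesis that yields the 28% used for sample size; no class-against-class test of 50% response is specified. This also stands.

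**There is a separate check.** Regressing status on baseline variables could show that none predicts it, so a false report is not inevitable. That stands in part: the likelihood ratio test rejected in 7-49% of null trials, above 5% throughout, and the plan does not say which test would support the Objective 2 claim.

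**It is exploratory.** The modelling sits under that label, and the primary outcome in section 11.0 (change in BPI worst pain) does not depend on it. This limits the severity.

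**Conclusion.** The concern holds in limited form. Section 11.0 does not exclude on-drug scores from the estimation of central status. On the plain reading, the class can be defined partly or largely by response, and a response difference between classes then says nothing about prediction from baseline. With a two-group response, a null trial can produce a class of about 30% whose response pattern resembles the one hypothesised, so the result could not tell the hypothesis from its absence.

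The size rests on assumed SDs and an assumed shape of change, and on reading Aim 2 as a joint fit with status regressed on baseline variables. Under that form the false class difference ran from 71% to 100% of trials in every setting tried. With phenotypes as indicators it depends on baseline separation: 5-9% at 1.2 SD, 50-61% at 0.7 SD. The documents do not support saying that the trial must reach a false conclusion. They support saying that this analysis, as written, cannot be relied on to answer Objective 2. Severity: should-fix.

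**What to change.** In section 11.0, state that:

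1. Centrality status, as a posterior probability or a score, is estimated from Visit 1 data only (cases and controls) and frozen before any Visit 2 score enters a model.
2. Aim 2 tests the frozen status as a predictor of week-5 change and of 50% response. It uses the posterior probability or a correction for classification error, and adjusts for baseline pain, since BPI severity is itself one of the phenotype measures.
3. Any joint fit that includes on-drug scores is descriptive. If a test from such a fit is reported, its reference distribution comes from permutation or its performance from cross-validation.

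The cost is SAP wording and a two-step program; no new visits or data are needed. Some efficiency is lost compared with a correctly specified joint model. Under the plan's own hypothesis the contrast is wide: 0.30 × 84 ≈ 25 central women with 0.70 × 25 ≈ 18 responders, against about 59 others with 0.10 × 59 ≈ 6.

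### The number of latent pain classes is decided by an AIC gap with no calibration for mixtures, and the false-positive rate depends on an ambiguous threshold

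*Combined protocol and SAP*

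**What the plan says.** Objective 1 (Section 3.0) is to assess whether pain centralization is present, and to what degree. The latent model for this stands in Section 11.0 under Exploratory analyses, Assessment of Centralized Pain. Centrality is a subject-level latent variable shared by several generalized linear models and fitted by EM. Continuous, ordered and binary forms are all to be explored.

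Models are compared by AIC: "A threshold of 2 per 1 degree of freedom will be applied to AIC differences". The plan treats this gap as its measure of a significant difference. It then selects the model with the highest AIC and uses it to predict each subject's status. The illustration in 199 patients applies the criterion to one class against two and reports that "the two-cluster model is significantly better than the homogeneous patient population".

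The Analysis paragraph turns to Aim 2, where "latent dichotomous pain centrality status will be hypothesized". A mixed model follows, with a random effect for the interaction between drug and centrality, and then: "Hypotheses will be tested by the likelihood ratio test". It states neither the hypotheses nor the reference distribution.

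The only error rates in the section belong to the responder-proportion test: "Overall, this leads to the expected 28% response rate", compared with 6% at a two-sided 0.05, and "we will have the power of 81% with 21 patients in each" bin.

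**The concern.** In a regular nested model, each redundant parameter raises twice the log-likelihood by about 1 on average, so the AIC penalty of 2 per parameter is protective. Comparing one regression with a mixture of two is not regular. If only one class exists, either the mixing weight lies on its boundary or the second regression is not identified. The EM fit can then search for any split of the sample that improves the likelihood, and the gain can exceed the penalty.

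The selected model is carried forward into each subject's predicted status. A spurious second class would therefore feed the answer to Objective 1 and any later analysis built on those predictions.

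**Working it through.** **1. The plan's own figure.** Expected response: 0.30 × 0.70 + 0.70 × 0.10 = 0.21 + 0.07 = 0.28. Arcsine power for 28% v 6%, n = 21, two-sided 0.05: 2√21 × (arcsin√0.28 − arcsin√0.06) − 1.96 = 2 × 4.583 × (0.5576 − 0.2475) − 1.96 = 0.882, and Φ(0.882) = 81.1%. This reproduces the stated 81%. It concerns responder proportions and says nothing about the latent-class step.

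**2. Parameters added by a second class.** The illustration uses eight scores (PainDETECT, age, BMI, depression, anxiety, sleep, fatigue, perceived stress) and a four-level treatment bin: 8 + 3 = 11 slopes. With a common variance, a second class adds 11 slopes + 1 intercept + 1 mixing weight = 13 parameters.

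**3. What the threshold could mean.** Let LR be twice the log-likelihood gain. The AIC gain is LR − 2 × 13.
- Lowest AIC wins: LR > 26.
- AIC better by a fixed 2 points: LR > 28.
- AIC gain above 2 per added parameter: LR − 26 > 26, so LR > 52.

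**4. Simulation with one true regression.** Assumptions not in the documents: a single normal response, independent normal covariates, common variance, EM with several random starts. Each setting used 200 to 300 samples, with Monte Carlo error up to about ±7 points. At n = 132 (84 cases + 48 controls):

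| Covariates | Added parameters | Lowest AIC picks two classes |
|---|---|---|
| 4 | 6 | 24% |
| 8 | 10 | 40% |
| 11 | 13 | 73% |

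The per-parameter reading gave 0% to 1% at this size. Another set of runs gave 37% to 53% under lowest AIC with 4 and 8 covariates, so the figures are approximate.

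A separate set with 11 covariates compared all three readings:

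| n | LR > 26 | LR > 28 | LR > 52 |
|---|---|---|---|
| 199 | 47% | 30% | 0% |
| 132 | 70% | 58% | 1% |
| 84 | 95% | 91% | 9–15% |

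**5. Why it happens.** The mean LR at n = 132 with 11 covariates was 30.3. Regular theory would give about 13, and the AIC penalty is 26. As a comparator, adding 13 known terms to an ordinary regression at n = 132 gives a false AIC preference in only 5% of samples, so most of the excess comes from the mixture.

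**6. Calibrated 5% cutoffs for LR.** With 11 covariates these are 38.3 (n = 199), 43.4 (n = 132) and 55.9 (n = 84). The cutoffs 26 and 28 fall below all three. The cutoff 52 is stricter than needed at 199 and 132, and slightly too lax at 84. At n = 84 with fewer covariates the calibrated values are 19.4 (6 added parameters) and 36.3 (10). Lowest AIC gives 12 and 20, which are too low. The per-parameter reading gives 24 and 40, which are stricter than needed.

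**7. Sensitivity at n = 132.** A rounded 0–10 response gave 71% under lowest AIC with 11 covariates. Class-specific variances gave 99.5%, and 5.5% under the per-parameter reading. With five covariates lowest AIC gave 32%, and with none 10%.

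**The case against.** The strongest reply is that the literal rule already protects. If the threshold is an AIC gain of 2 for each added parameter, false classes are rare at n = 132, the stated Aim 1 size, and the rule is stricter there than a 5% bootstrap test. This stands for that reading. But the next sentence of the plan simply selects the best model on AIC, and the illustration reports no AIC gap, so the text does not fix the reading.

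A reader might infer that the plan tests the number of classes with an ordinary chi-square likelihood ratio test and so breaches a stated 5% level. The documents do not support that:
- The likelihood ratio sentence belongs to the Aim 2 mixed model, where a dichotomous status is assumed.
- No chi-square reference is named. The 0.05 is stated only for the responder test.
- AIC itself uses no chi-square reference.
- A likelihood ratio test of fixed effects, with the class structure given, is regular.

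It is also fair that the section is headed exploratory, that the plan favours continuous centrality, and that the case-control comparison serves Objective 1 as well. The planned model shares one latent variable across several responses, which the simulation did not reproduce. These points limit the weight and precision of the finding. They do not supply a calibration.

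**Conclusion.** The point holds in a limited form. Section 11.0 judges whether latent classes exist by an AIC difference read as significance, with no calibration for a comparison where the usual theory fails. At n = 132 and with no true classes, the false-positive rate is about 24% to 73% under lowest AIC with 4 to 11 covariates, and about 0% to 1% under the per-parameter reading.

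These sizes rest on the simulation assumptions above and depend strongly on the number of covariates. They do not show that the two clusters in the 199-patient illustration are spurious. The direction of the criterion also needs stating: the plan picks the highest AIC, whereas under the usual definition the lowest is best. The missing hypotheses and reference distribution for Aim 2 are a gap in specification, not a demonstrated error. Should-fix.

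**What to change.** In Section 11.0, Assessment of Centralized Pain:
- Decide one class against two or more by a parametric bootstrap likelihood ratio test. Simulate from the fitted one-class model (for example 1,000 data sets), refit both models each time, and compare the observed LR with that distribution.
- Use AIC only to compare models within a fixed number of classes. State its definition, whether lower or higher is better, and exactly what the threshold of 2 applies to.

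In the Analysis paragraph for Aim 2:
- List the hypotheses that the likelihood ratio test addresses, and the reference distribution for each.
- Use a bootstrap reference for any test of the latent drug-by-centrality random effect. Tests of fixed effects with the class structure given can stay as they are.

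The cost is SAP wording and computing time, and possibly fewer positive class findings than under lowest AIC. The sample size and the 81% power figure do not change.
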